### **6.2.5 Conventions for Missing and Partial Dates**

All rules explained below for partial/missing dates will be followed unless contradicted by any other data recorded on the electronic Case Report Form (eCRF).

All dates presented in the individual subject listings will be as recorded on the eCRF (i.e., not completed as per the below rules).

### **6.2.6 Missing/Partial Start/Stop Date of AEs and Concomitant Medications**

Missing and partial start and stop date will be imputed for analysis purposes as follows

Partial or missing stop date will be imputed as follows:

- If the stop date is completely missing and the event has resolved or the subject has stopped taking the concomitant medication, the stop date will be imputed as the date of the subject's last clinic visit in the study.
- If only the year is known, the stop date will be imputed as "31-Dec" of that year or as the date of the subject's last clinic visit in the study if in the same year.

- If the month and year are known, the stop date will be imputed as the last day of that month unless the stop date corresponds to the same month as the subject's last clinic visit in which case the date of subject's last clinic visit in the study will be used instead.

Missing start date will be imputed as follows:

- If the stop date occurs on or after the start of study drug or the event/concomitant medication is ongoing, the start date will be imputed as the date of the first dose of study drug.
- If the stop date occurs before the start of study drug, the start date of the event/concomitant medication will be imputed as the subject's screening date or the stop date of the event/concomitant medication whichever is earlier.

Partial start date (year present, but month and day missing)

- If the stop date occurs on or after the start of study drug or the event/concomitant medication is ongoing, and the year is the same as the year of first dosing the start date will be imputed as "01-Jan" of the same year or the date of the first dose of study drug whichever is latest. If the year is different from the year of first dosing "01-Jan" will be used.
- If the stop date occurs before the start of study drug, the start date of the event/concomitant medication will be imputed as the "01-Jan" of the same year.

Partial start date (month and year present, but day missing)

- If the stop date occurs on or after the start of study drug or the event/concomitant medication is ongoing, the start date will be imputed as the first day of the same month and year unless this partial start date is in same month as the first dose of study drug in which case the date of first dose of study drug will be used.
- If the stop date occurs before the start of study drug, the start date will be imputed as the first day of the month and year of the partial stop date.

### **6.2.7 Missing Last Dates of Study Drug Dosing**

If the date of last dose of study drug is completely missing, then the date of last dose of study drug will be taken for analysis purposes as the date when the subject would have run out of study drug assuming full compliance from the date the study drug was last dispensed or the date of subject's last clinic visit in the study or early withdrawal or death whichever is earlier.

If only the month and year of the last dose was recorded, then the date of last dosing will be taken for analysis purposes as the date the subject would have run out of study drug assuming full compliance from the date the study drug was last dispensed, the last day of the month of the recorded last dose or the date of subject's last clinic visit in the study or early withdrawal or death whichever the earlier.

### **6.2.8 Missing Diagnosis Dates**

If the month and year are present but the day is missing, the diagnosis date will be set to first day of the relevant month. If only the year is recorded the diagnosis date will be set as "01-Jan" for that year.

### **6.2.9 Exposure to Study Drug**

Exposure to study drug will be calculated from the date of last dosing minus the first day of dosing + 1 for each prescribing record. Exposure will be summarized as the number of days on medication and mean daily dose. Mean daily dose will take into account periods where zero dose was prescribed.

### **6.2.10 Electrocardiogram Data**

For ECG data recorded on continuous scales, if more than one value is recorded at a time point, the mean value rounded to the integer will be presented. For overall interpretation if more than one value is recorded, the most severe (worst case) of the respective readings will be taken.

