### **6.2.3 Early Terminations Assessments**

Data collected at Early Termination (ET) assessments will be mapped to the visits closest to the date of termination.

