### **6.2.11 Unscheduled Visits**

All visits whether scheduled or unscheduled will be mapped to the closest scheduled protocol visit according to the protocol schedule of assessments. However, visits, when sorted by visit number and visit date, must remain in chronological order. In summary tables by visit, a subject's latest observation per visit will be tabulated. For assessments of continuous periods of remission, all available observations will be used.

All assessments will be listed in the relevant appendices to the CSR.

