### **6.2.12 Randomization Strata**

The randomization will be stratified by biopsy class (Class V only versus Others) and by prior MMF use at time of screening. A regional blocking factor will also be used for supply purposes ensuring balance within region. The stratification factors and the regional blocking factor will be used as covariates in the primary analyses.

Tables of events or medications will be ordered in descending frequency of subjects followed by (where applicable) events for the higher level term (system organ class or ATC levels 4 and 2) followed by the preferred term. Ordering will be for the VCS treatment group first followed by the placebo group and alphabetical thereafter.

Listings will be sorted in the following order treatment group, subject, parameter, and visit unless otherwise stated. All data will be listed, subjects who were not randomized will be displayed after the randomized treatment groups.

Continuous variables will be summarized by the number of non-missing observations, mean, median, standard deviation, and minimum and maximum. For all tabulations of changes from baseline data, the lower and upper 95% confidence limits for the mean for the individual treatments will be given.

Categorical variables will be summarized by presenting the frequency and percent. Percentages will be based on the number of non-missing observations out of the subject population unless otherwise specified. For each variable, all categories will be shown. Zero frequencies (but not the percent) within a category will be presented.

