### **6.13.4 Electrocardiogram Data**

Descriptive statistics for observed values and changes from baseline in the following ECG variables at screening, Week 12, Week 24, and Week 52 will be tabulated at each follow-up:

- Heart rate (bpm)
- PR interval (ms)
- QRS complex (ms)
- QT interval (ms)
- QTc interval (ms)
- QTcF interval (ms)

Shift tables in relation to the overall interpretation (Normal, Abnormal NCS, and Abnormal CS) from baseline to each follow-up visit will be presented. Listings of all ECG measurements will be provided.

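### The latest-value rule in SAP 6.2.11 lets a recovery ECG replace a confirmed QTcF above 500 msec, or more than 60 msec over baseline, in the by-visit ECG table

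*SAP*

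**What the plan says.** SAP 6.2.10 has two rules for repeated ECG readings. For continuous measures, "if more than one value is recorded at a time point, the mean value rounded to the integer will be presented". For the overall interpretation, "the most severe (worst case) of the respective readings will be taken".

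SAP 6.2.11 covers unscheduled assessments: "All visits whether scheduled or unscheduled will be mapped to the closest scheduled protocol visit". In by-visit summaries the subject's "latest observation per visit will be tabulated". The section makes an exception for periods of remission, which use every observation. It makes none for ECGs. SAP 6.2.3 adds that "Data collected at Early Termination (ET) assessments will be mapped to the visits closest to the date of termination".

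SAP 6.13.4 plans "Descriptive statistics for observed values and changes from baseline in the following ECG variables at screening, Week 12, Week 24, and Week 52", shift tables of the overall interpretation, and this: "Listings of all ECG measurements will be provided". The SAP's general conventions (in the supplied copy they follow 6.2.12) state that "Continuous variables will be summarized by the number of non-missing observations, mean, median, standard deviation, and minimum and maximum", so the by-visit table carries a maximum.

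Protocol 9.1.4.1 supplies the sequence of ECGs. A QTcF above 500 msec, or more than 60 msec over baseline, leads to an unscheduled visit within 24 hours, with three tracings taken inside one minute. If the excess is confirmed, the subject stops study treatment. QTcF is then followed until it returns to baseline or the investigator judges further evaluation unnecessary.

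**The concern.** The protocol treats these two QTcF limits as mandatory reasons to stop study treatment, and ECG change from baseline is a named safety endpoint in Protocol 13.9. A reader of the by-visit table would expect a confirmed crossing to show in the maximum and in the change from baseline.

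The latest-value rule works against that. Follow-up after a confirmed event is meant to continue until QTcF has come down, so the last ECG mapped to the visit tends to be the recovered one, taken off study treatment. The SAP keeps the worst reading for the interpretation category but not for the QTcF number on which the protocol acts. At stake is how faithfully the safety summary shows these events. Efficacy inference and the management of subjects during the trial are not affected.

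**Working it through.** The plan gives no figure to reproduce. The check traces the rules and then applies them to assumed values.

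**1. How the rules fit together.** The protocol's triplicate is a set of replicates at one time, so 6.2.10 reduces it to one session mean. 6.2.11 then chooses among the sessions mapped to a visit and takes the latest. This reading makes both rules workable, and it is used below.

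**2. Which ECGs can share a visit.** The inputs are the nominal visit weeks in the Schedule of Events. Under nearest-visit mapping, the boundary is half the gap to the next visit:

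- Week 12 to 16: 28 days / 2 = 14 days.
- Week 24 to 30: 42 days / 2 = 21 days.
- Week 52 to 56: 28 days / 2 = 14 days.

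A recheck within 24 hours falls well inside these limits. A recovery ECG does so if it is taken within about two weeks of Week 12 or 52, or three weeks of Week 24. These are nominal figures: actual visit dates vary within the permitted windows, and 6.2.11 also requires visits to stay in chronological order. A recovery ECG beyond the boundary maps to a later visit and leaves the confirmed value in place. At Week 52 treatment is ending anyway, so stopping it adds little there.

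**3. When a crossing disappears.** Let B be the baseline and L the latest session mapped to the visit. The table shows L and L − B.

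- The crossing of 500 msec is lost if L ≤ 500.
- The crossing of +60 msec is lost if L ≤ B + 60.

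**4. Worked cases.** All values are in msec and assumed. The confirmed value is the triplicate mean.

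| Case | B | Scheduled ECG | Triplicate | Confirmed | Later ECG | Table shows |
|---|---|---|---|---|---|---|
| A1 | 440 | 512 (+72) | 503, 505, 507 | 1515/3 = 505 (+65) | none | 505 (+65) |
| A2 | 440 | 512 (+72) | 503, 505, 507 | 505 (+65) | 450 | 450 (+10) |
| B | 420 | 485 (+65) | 484, 486, 485 | 1455/3 = 485 (+65) | 460 | 460 (+40) |
| C | 420 | 505 (+85) | 508, 512, 510 | 1530/3 = 510 (+90) | 495 | 495 (+75) |

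A1 shows that the event stays visible when nothing later maps to the visit. In A2 both crossings are lost; with B = 440, any later value of 500 or below does this, since 440 + 60 = 500. In B the only crossing, +60, is lost. In C the 500 crossing is lost but the +60 crossing remains.

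**5. The Early Termination route.** The Schedule of Events (footnote 2) sends subjects who discontinue study treatment to an Early Termination visit, whose assessments include an ECG. Protocol 9.1.4.1 instead keeps a subject who stops treatment for QTcF on the remaining scheduled visits. If an Early Termination ECG is done, 6.2.3 maps it to the nearest visit and it can replace the confirmed value in the same way. The recovery ECG does not depend on this route.

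**The case against.** By-visit descriptive tables show central tendency and are not meant to screen for outliers. Protocol 13.9 promises ECG change from baseline, and the SAP delivers it. The events also surface elsewhere: every ECG is listed, discontinuations are tabulated by arm and visit (SAP 6.4), adverse events leading to discontinuation are summarised (6.13.1), and the interpretation shift tables use the worst reading. SAP Section 6 allows further tables in the study report.

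Much of this stands, and it is why the point is minor. It does not remove the point. Listings give no comparison between arms. The discontinuation counts, as described, do not isolate QTcF. The shift tables help if the worst reading is taken over all ECGs mapped to the visit; if it is taken within a session, as the mean is here, the later tracing replaces it too. In either case the category shows neither QTcF nor its size.

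Three stronger readings are tempting, and the documents do not support them:

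- **That the two rules conflict**, so that trigger, triplicate and recovery tracings might all be averaged together. This would require treating a whole mapped visit as one time point, which neither section says.
- **That the SAP plans no count of subjects past a QTcF limit.** Section 6.13.4 describes none, but the contents of the Section 11 table list are not in the supplied text, nor are the headings from 6.2.13 to 6.3. Such a count, or a convention on session selection, may be there.
- **That subjects are less protected.** The protocol acts on individual readings, whatever is tabulated later.

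**Conclusion.** The point holds as a minor defect in safety reporting. On the reading that reconciles 6.2.10 with 6.2.11, a recovery ECG mapped to the same visit replaces a confirmed QTcF crossing in the 6.13.4 numeric table. The subject's contribution to the maximum and to the change from baseline is then the recovered value. This follows from a stated rule, not only from missing detail.

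The loss is conditional. It needs a later ECG inside the mapping window and at or below the limits in step 3 of the working; otherwise the confirmed event remains in the table. The documents give no rate of crossings and no time course of recovery, so the number of subjects affected cannot be estimated, and the QTcF values above only illustrate the mechanism. The conclusion also assumes that no convention in the unsupplied SAP text exempts ECGs from the latest-value rule.

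**What to change.** In SAP 6.2.10, limit averaging to replicates from one recording session. In 6.2.11, state that by-visit ECG tables use the scheduled-visit session and not the latest one mapped there. In case A2 the Week 12 entry would then be 512 (+72).

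Take QTcF extremes from each subject's worst post-baseline session value over all scheduled, unscheduled and Early Termination ECGs, so that a crossing first seen at an unscheduled visit is also kept. In 6.13.4, count subjects by arm with any value above 500 msec and any increase above 60 msec on that basis, with protocol-confirmed cases in a separate row.

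If Section 11 already lists such a count, only the wording on session selection and worst values is needed. The cost is a few sentences and at most one table from data already collected. Unconfirmed single readings will raise the counts slightly, which the separate confirmed row makes clear.

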### **6.2.11 Unscheduled Visits**

All visits whether scheduled or unscheduled will be mapped to the closest scheduled protocol visit according to the protocol schedule of assessments. However, visits, when sorted by visit number and visit date, must remain in chronological order. In summary tables by visit, a subject's latest observation per visit will be tabulated. For assessments of continuous periods of remission, all available observations will be used.

All assessments will be listed in the relevant appendices to the CSR.

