### **7.6.1 Deterioration in Renal Function**

Serum creatinine and eGFR utilizing the CKD-EPI formula will be used for the assessment of renal function at every visit (Visits 1-15 and unscheduled visit(s)). Subjects will have a minimum of 2 eGFR measurements conducted prior to dosing at Visit 2. The lowest of the pre-dose eGFR assessments will be used as the marker of baseline renal function.

It is recognized that eGFR may be unreliable at higher values ( $>100$  mL/min/1.73 m^2). Lupus nephritis subjects with nephrotic range proteinuria frequently have wide fluctuations in serum creatinine (and therefore eGFR) which are not representative of true renal dysfunction. Chronic kidney disease is defined as eGFR  $<60$  mL/min/1.73 m^2 for  $\geq 3$  months [20], with or without kidney damage.

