#### **7.6.1.1 Decrease in eGFR $>30\%$ and eGFR $<60$ mL/min/1.73 m^2**

During the treatment period, any subject experiencing a  $>30\%$  decrease in eGFR from baseline to  $<60$  mL/min/1.73 m^2, will have study treatment interrupted until a repeat test can be performed (unscheduled visit to be completed). If the decrease is confirmed and not due to potential contributing factors (e.g., high baseline eGFR, the addition or modification of non-steroidal anti-inflammatory drugs (NSAIDs), angiotensin converting enzyme (ACE) inhibitors, angiotensin II receptor blockers (ARBs), a concurrent state of dehydration, overdosing with study treatment, lupus renal flare, etc.), the case should be discussed with the

Medical Monitor, the study treatment should be withheld, and eGFR retested within 48 hours. If the eGFR decrease is not confirmed, the study treatment can be restarted at 2 capsules BID and increased as tolerated with discussion with the Medical Monitor.

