### **9.2.5 Unscheduled Visit**

Unscheduled visits may be performed during the course of the study for safety reasons. An unscheduled visit is required 2 weeks after dose reduction at any time during the study. Only the data relevant to the purpose of the visit will be collected in the source documents and eCRF. An unscheduled visit is requested in the following cases:

- QTcF value exceeding 500 msec, or an increase  $>60$  msec from baseline, where the ECG will be repeated (confirmed) at an unscheduled visit
- Systolic BP is  $\geq 165$  mmHg or diastolic BP is  $\geq 105$  mmHg, or confirmed systolic BP  $>130$  mmHg or a diastolic BP  $>80$  mmHg
- Decrease in eGFR  $>30\%$  compared to baseline, or a confirmed decrease in eGFR  $>20-30\%$  compared to baseline
- Complete blood count must be performed locally at Weeks 1 and 3 in subjects not already taking MMF at the Screening Visit

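### By-visit eGFR and creatinine tables take the latest value mapped to each visit, so a prompt recheck after a drug hold can replace the on-drug value that triggered it

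*SAP*

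**What the plan says.** SAP 6.2.11 sets two rules. The first is on mapping: "All visits whether scheduled or unscheduled will be mapped to the closest scheduled protocol visit according to the protocol schedule of assessments". The second is on selection: "In summary tables by visit, a subject's latest observation per visit will be tabulated". The one exception is for remission periods: "For assessments of continuous periods of remission, all available observations will be used". Values that are not tabulated are kept in listings: "All assessments will be listed in the relevant appendices to the CSR". No exception is made for rechecks or for values taken while study drug is held or reduced.

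The Protocol decides when unscheduled renal tests happen:

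- Section 7.6.1 has creatinine and eGFR assessed at unscheduled visits as well as scheduled ones.
- Section 7.6.1.1: a subject whose eGFR falls by more than 30% to below 60 mL/min/1.73 m² "will have study treatment interrupted until a repeat test can be performed (unscheduled visit to be completed"). If the fall is confirmed without another explanation, drug is withheld and eGFR is tested again within 48 hours.
- Section 7.6.1.2: a fall of more than 20% and up to 30%, to below 60, is rechecked in about 2 weeks. Dose action is optional.
- Section 9.2.5: "An unscheduled visit is required 2 weeks after dose reduction at any time during the study".

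Protocol 2.1 describes the renal risk as dose-related and reversible.

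**The concern.** Picking the latest value is harmless when repeat tests happen for reasons unrelated to the result. Here the repeat exists because the scheduled value was poor, and the drug suspected of causing it has been stopped in between. The later value is expected to be better, both because the effect is described as reversible and through regression to the mean. It then stands in the table as the value for that visit.

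The tables exposed are change from baseline in serum creatinine and in eGFR (SAP 6.11.4.4 and 6.11.4.6) and the laboratory summaries and shift tables (SAP 6.13.2). Table 14.2.7, the proportion with a confirmed fall above 30% (SAP 6.11.4.2), is exposed if it is built from one value per visit. A recovered value can then break the required pair of consecutive time points.

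More triggers are expected on voclosporin. In Phase 2, eGFR fell by a median of 8-9 mL/min by Week 4 on voclosporin (Protocol 1.2.4.2). Decreased GFR led to permanent discontinuation in 1 (1.1%) placebo, 6 (6.7%) low-dose and 5 (5.6%) high-dose subjects (Protocol 1.2.5). At stake is a renal safety comparison for a calcineurin inhibitor that leans towards no difference, most of all in the tail.

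**Working it through.** The plan gives no figure on this point to reproduce. The check has three steps.

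**1. Which rechecks map back?** On nominal dates, a recheck maps back to its triggering visit when its delay is less than half the gap to the next scheduled visit. Visits are at Weeks 2, 4, 8, 12, 16, 20, 24, 30, 36, 42, 48, 52 and 56 (Schedule of Events).

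| Triggering visit | Gap to next visit | Half-gap | Recheck at +2 or +4 days | Recheck at +14 days |
|---|---|---|---|---|
| Week 2 | 14 days | 7 days | maps back | maps forward to Week 4 |
| Weeks 4, 8, 12, 16, 20 | 28 days | 14 days | maps back | exact tie |
| Weeks 24, 30, 36, 42 | 42 days | 21 days | maps back | maps back |
| Weeks 48, 52 | 28 days | 14 days | maps back | exact tie |

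Prompt rechecks map back at 12 of 12 visits. Rechecks at exactly 2 weeks map back at 4, tie at 7 and map forward at 1. SAP 6.2.11 has no tie rule. A recheck mapped forward is normally followed by that visit's scheduled value, so it displaces nothing.

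**2. Effect on a visit mean.** Bias in one arm's mean = share of subjects overwritten × mean recovery at recheck. Neither input is in the documents. Assuming 2-10% overwritten and 5-20 mL/min recovery:

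- low end: 0.02 × 5 = 0.1 mL/min, and 0.1/9 = 1% of the Phase 2 fall
- high end: 0.10 × 20 = 2.0 mL/min, and 2.0/8 = 25% of it

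**3. Effect on the tail.** I simulated one visit with 400,000 subjects per arm. The assumptions below are mine and not the documents':

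- True baseline eGFR has mean 88 and SD 28, limited to 46-140. The analysis baseline is the lower of two measurements.
- The proportional fall has mean 9.5% on voclosporin and 0% on placebo, with SD 12% in both arms.
- Measurement CV is 6% or 10%.
- Recovery at recheck is 0%, 50% or 100% of the loss on voclosporin, and none on placebo.
- Every subject with a fall above 30% to below 60 has a recheck that maps to the same visit.

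The trigger fires in 2.5% (CV 6%) to 3.4% (CV 10%) of voclosporin subjects and in 0.4% to 0.9% of placebo subjects. Each cell shows scheduled value → latest value.

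| CV | Recovery | Mean arm difference (mL/min) | Fall >30%, voclosporin | Fall >30%, placebo | Arm difference (points) |
|---|---|---|---|---|---|
| 6% | 0% | -8.42 → -8.38 | 4.3% → 3.4% | 0.8% → 0.6% | 3.5 → 2.8 |
| 6% | 50% | -8.42 → -8.08 | 4.3% → 1.8% | 0.8% → 0.6% | 3.5 → 1.2 |
| 6% | 100% | -8.42 → -7.78 | 4.3% → 1.8% | 0.8% → 0.6% | 3.5 → 1.2 |
| 10% | 0% | -8.42 → -8.29 | 5.9% → 4.1% | 1.6% → 1.0% | 4.3 → 3.1 |
| 10% | 50% | -8.42 → -7.93 | 5.9% → 2.7% | 1.6% → 1.0% | 4.3 → 1.7 |
| 10% | 100% | -8.42 → -7.57 | 5.9% → 2.5% | 1.6% → 1.0% | 4.3 → 1.5 |

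The mean difference shrinks by between (8.42 - 8.38)/8.42 = 0.5% and (8.42 - 7.57)/8.42 = 10%. With 162 voclosporin subjects, the expected count with a fall above 30% goes from 7.0-9.6 (4.3% and 5.9% of 162) to 2.9-6.6 (1.8% and 4.1% of 162).

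**The case against.** The case for leaving the rule alone has substance, and much of it limits the scope.

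- **The size is assumed.** The documents give no rate of holds, recheck timing or recovery. Counts fall even with no recovery, so part of the drop is regression to the mean. The terminal half-life is at least 30 hours (Protocol 1.2.4.1), so 48 hours off drug is at most 48/30 = 1.6 half-lives and recovery may be partial. This stands.
- **The 2-week visits matter less than they seem to.** Phase 2 placed the fall by Week 4, where a 2-week recheck ties or maps forward. Falls of 20-30% may be rechecked at full dose. This stands. The prompt rechecks after a hold carry the point.
- **The signal is reported elsewhere.** Adverse events, discontinuations, dose changes and listings remain. True, but none of these compares the on-drug eGFR distribution between arms.
- **Text not seen.** SAP 6.2.13 (eGFR) and the table list in SAP section 11 were not available to this review. A special eGFR rule or a worst-value table may be there. Only central-laboratory results are analyzed (SAP 6.13.2), so local rechecks displace nothing.

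A reader might also infer more than the documents support:

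- **Blood pressure.** Protocol 7.9 holds drug only for marked values with symptoms. A confirmed reading above 130/80 is managed by local practice (Protocol 9.1.3.1).
- **UPCR.** Protocol 9.2.5 limits collection at unscheduled visits to what serves the visit's purpose, so a UPCR sample is not established.
- **Removal from the active arm only.** The rule is the same in both arms, and placebo counts fall too in the table above. The imbalance comes from the expected trigger rate.

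**Conclusion.** The point holds for eGFR and serum creatinine. As written, SAP 6.2.11 lets a prompt central-laboratory recheck, taken after study drug is interrupted under Protocol 7.6.1.1, replace the on-drug value in by-visit summaries and shift tables. The direction is towards understating the on-drug renal effect. That rests on two things: more triggers on voclosporin, and the reversibility that the Protocol itself states. The effect on means is probably small, and the effect on counts of large falls is larger in relative terms. The figures above illustrate this and are not estimates.

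It would be wrong to conclude that the primary result is biased. The CEC adjudicates from the eGFR data (SAP 6.11.2.1), and confirmation needs two consecutive measures at least 3 days apart (SAP 6.11.1). SAP 6.2.11 speaks of summary tables by visit. Nor can it be said that the MMRM is biased, because the SAP does not state which value enters it. That silence, and the missing tie rule, should be closed in the same edit.

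**What to change.** In SAP 6.2.11:

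1. Tabulate the scheduled-visit value. Use an unscheduled value, the one closest to the target day and with a stated tie rule, only when the scheduled value is missing.
2. State that the MMRM uses the same selection.
3. Derive confirmed eGFR falls above 30% (Table 14.2.7) from all observations. A fall that recovers off drug would still count as unconfirmed, so item 4 is needed beside it.
4. Add by-arm summaries of the lowest post-baseline eGFR and the highest post-baseline creatinine, using all scheduled and unscheduled values, unless SAP 6.2.13 or the table list already provides them.

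SAP 6.2.10 already gives repeat ECG readings a deliberate rule (the mean, or the worst case for interpretation), so this is in keeping with the SAP.

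The cost is a few sentences, a changed visit-selection flag and one or two extra tables. No new data are needed, and no clinical management rule changes.
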